2.2 BACKGROUND

The opioid overdose epidemic. The United States is in the midst of an epidemic of prescription drug overdose deaths, with deaths associated with prescription pain relievers of particular concern.¹ Drug overdose has become the second leading cause of accidental death in the United States.² Opioids are currently the most commonly prescribed class of medications in the United States.³ Since 2000, the rate of deaths from drug overdoses has increased 137%, including a 200% increase in the rate of overdose deaths involving opioids (opioid pain relievers and heroin).⁴ Inappropriate prescribing of opioids has driven this unprecedented opioid epidemic, and the Centers for Disease Control and Prevention has strongly recommended fundamental changes in prescribing practices in order to address this public health emergency.⁵

Dentists frequently prescribe opioids for pain management following tooth extractions. Opioid analgesics are among the most frequently prescribed drugs by dentists.⁶ For example, an estimated 5 million people undergo third-molar extractions in the United States each year, resulting in postoperative pain, swelling, and discomfort, even when surgical complications are not present.⁷ The resulting postoperative pain lasts, on average, 3 to 5 days, and a multipronged approach to pain management often includes icing the jaw to reduce swelling, as well as some analgesics for pain relief. Many patients younger than 25 years are introduced to prescription opioids via postoperative dental pain management following third-molar surgery or wisdom tooth extraction.⁸ Recent evidence shows that exposure to opioid analgesic prescriptions following dental procedures are increasing over time.⁹

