Potential risks to patient participants are considered minimal. For patients in all study arms, there is a potential breach of privacy of individually identifying study data. To minimize this risk, no individually identifying patient information will be made available in publication or dissemination efforts. Results that are shared will be in aggregate form.

For patients whose providers are exposed to the CDS, there are several additional potential risks. First, the CDS may not display all relevant clinical information about the patient, as the CDS is limited to what is contained in the EHR. Second, it is possible that the CDS could erroneously attribute a condition or drug to a patient based on the EHR. In the design phase, the study team will seek and feedback from multiple sources to ensure that the content and CDS firing is as accurate and appropriate as possible. Before implementation, several investigators will review and test the CDS firing to optimize the information displayed. Provider training will inform providers of these limitations and offer strategies to further minimize these risks. Throughout the implementation phase, the study team will request feedback from providers using the CDS to identify any issues and modify the CDS, if needed.

Third, the CDS may be inappropriate for a given individual patient and, if applied without further checking the clinical status of a given patient, could lead to erroneous therapy, adverse events, disability, or death. However, the clinical recommendations are personalized based on the patient's medical problem list, allergies and current medications. The risk of untoward consequences from such clinical actions is considered minimal. Moreover, this potential risk is routinely present in every clinical encounter in the health care system. Fourth, the potential shift in provider prescribing and/or pain management recommendations may also have unintended consequences on patients' post-procedure pain management. It is possible that this shift could cause under-controlled pain. Providers encounter this in current dental practice and will address it in a similar fashion consistent with the reasonable standard of care.

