7 STUDY INTERVENTION DISCONTINUATION AND PARTICIPANT DISCONTINUATION/WITHDRAWAL

7.1 DISCONTINUATION OF STUDY INTERVENTION

Providers should exercise clinical judgment and can at their discretion disregard any information the CDS offers. As such, patients will receive usual dental care, regardless of study arm.

Hospitalizations documented within the HealthPartners electronic health record that occur within a 72-hour window following the index extraction encounter will be chart reviewed for severity and relatedness on a quarterly basis during the intervention period by Co-investigator and/or PI [name]. These hospitalizations rates will be compared at a frequency determined by the DSMB or quarterly whichever is greater.

Based on the relevant data, the study team in consultation with the DSMB would determine whether the study intervention needed to be modified or discontinued.

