8 STUDY ASSESSMENTS AND PROCEDURES

8.1 EFFICACY ASSESSMENTS

Primary Objective

To test the efficacy of two interventions (Clinical Decision Support with and without Patient Education), compared to treatment-as-usual to decrease opioid prescribing for dental extractions.

Data source: HealthPartners electronic health record

Procedures:

1. Gather extraction procedure records performed prior to and post CDS implementation
2. Gather opioid medication orders placed within 7 days of extraction procedure
3. Retrieve patient and provider descriptive data

Secondary Objectives

To test the efficacy of two interventions (Clinical Decision Support with and without Patient Education), compared to treatment-as-usual to increase exclusive non-opioid pain management for dental extractions.

Data source: HealthPartners electronic health record

Procedures:

1. Gather extraction procedure records performed prior to and post CDS implementation
2. Gather non-opioid medication recommendations given within 7 days of extraction procedure
3. Gather patient and provider descriptive data

To compare the degree to which each of the 3 study arms (Clinical Decision Support with and without Patient Education, and treatment-as-usual), facilitates shared provider and patient decision-making concerning pain management options for dental extractions.

Data source: Telephone administered patient survey responses

Procedures:

1. CESR staff will administer the survey by telephone
2. CESR staff will input patient responses into RedCap
3. Data will be exported and provided to the statistician

To explore whether the study interventions lead to differences in patient experiences of post-extraction pain. Data source: Patient survey

Procedures:

1. CESR staff will administer the survey by telephone
2. CESR staff will input patient responses into RedCap
3. Data will be exported and provided to the statistician

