8.2 SAFETY AND OTHER ASSESSMENTS

The study does not include objectives or endpoints concerning safety. However, the monitoring activities described below will be conducted to assess possible harm.

Identify whether the CDS inappropriately fires or inappropriately offers considerations

Data source: Provider report to alert study team about potential issues or concerns

Procedures:

1. Providers randomized to an intervention arm will be offered training.

2. They will be instructed to notify the study team when clinical judgement differs from the CDS
3. Notification options: (a) Contact Co-Investigator [name] or PI [name]; (b) select a "feedback" button contained within the CDS

Identify potential adverse events

Data source: HealthPartners electronic health record

Procedures:

1. Gather hospitalizations, emergency department visits, observational bed, and subsequent opioid prescribing made within 3 days post-extraction procedure

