8.3.4 TIME PERIOD AND FREQUENCY FOR EVENT ASSESSMENT AND FOLLOW-UP

Since there are no routine research contacts for all eligible patient participants, we will collect information from the electronic health record about hospitalizations, emergency department visits, observational bed, and subsequent opioid prescribing made within 3 days post-extraction procedure. This is consistent with the usual care delivery pathways and workflows related to dental procedures.

For the sub-sample of patients reached as part of survey data collection, CESR staff provides information to call their dental provider with questions or concerns. In this manner, the study team will not interfere with existing patient-provider communication, but rather support usual care.

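### Systematic harm capture ends 72 hours after extraction, the lower end of the protocol's own 3-to-5-day pain duration, so later acute-care visits are not systematically collected or compared by arm

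*Combined protocol and SAP*

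**What the plan says.** Four sections define harm monitoring from the electronic health record, and all four close it at the same point.

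- **7.1** sets its scope as "Hospitalizations documented within the HealthPartners electronic health record that occur within a 72-hour window following the index extraction encounter". Each quarter the charts of these cases are reviewed for how severe they are and whether they are related. Their rates are then compared at least quarterly, and the study team, consulting the DSMB, decides whether the intervention should be modified or discontinued.
- **8.2** is broader in event type but not in time: "Gather hospitalizations, emergency department visits, observational bed, and subsequent opioid prescribing made within 3 days post-extraction procedure".
- **8.3.4** repeats that list for adverse-event assessment, again ending with "subsequent opioid prescribing made within 3 days post-extraction procedure". Its reason for the approach is that it fits how dental care is usually delivered. It does not mention how long pain lasts.
- **9.4.4** summarises by arm only the hospitalisations within 72 hours that are judged to be adverse events.

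On the harm itself, section 2.3.1 says of the expected change in prescribing: "It is possible that this shift could cause under-controlled pain". Section 8.3.3.3 counts poorly managed pain, drug interactions and analgesic side effects as expected adverse events. On duration, section 2.2 says of third-molar extractions: "The resulting postoperative pain lasts, on average, 3 to 5 days".

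Other parts of the plan look later than day 3. Section 8.1 has the instruction "Gather opioid medication orders placed within 7 days of extraction procedure", and the survey in sections 1.3 and 9.1 asks about pain 3 to 6 days after the extraction.

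**The concern.** The trial sets out to reduce opioid prescribing and is powered on a fall from 40% to 15% in the intervention arms (section 9.2). The harm that could follow is pain that is not adequately controlled, or side effects of the analgesics used instead. Either could lead to an emergency visit, an observation stay or an admission. On the protocol's own figure, a patient of average duration may still be in pain when the harm window closes.

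The 72-hour hospitalisation comparison is the one that section 7.1 describes before turning to modification or discontinuation, and it is the only adverse-event summary by arm in section 9.4.4. If it shows similar rates, a reader would want to conclude that less opioid prescribing did not send more patients to acute care. A window that may end before the pain does supports that conclusion only for the first three days.

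**Working it through.** The plan states no figure for the adequacy of this window, so there is nothing to reproduce. The check sets the window against the stated duration and then asks what covers the remaining days.

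**1. Window against pain duration.** Inputs: window 3 days (7.1, 8.2, 8.3.4, 9.4.4); average pain duration 3 to 5 days (2.2). Share of the pain period inside the window = 3 / duration.

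| Pain duration (days) | Share inside window | Share outside |
|---|---|---|
| 3 | 3/3 = 100% | 0% |
| 4 | 3/4 = 75% | 25% |
| 5 | 3/5 = 60% | 40% |

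This needs no assumption about how duration varies between patients. It describes time in pain, not visits.

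**2. What reaches past day 3.**

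| Source | Reach | Systematic count of acute-care visits? |
|---|---|---|
| Serious adverse event reports (8.3.6) | No time limit stated | No; depends on someone noticing and reporting |
| Stored encounters after the index visit (6.3) | Not limited in the text | No; no analysis after 72 hours is specified |
| Opioid orders (8.1) | 7 days | No; gathered as efficacy data, and orders are not visits |
| Pain survey (1.3, 9.1, 9.2) | Days 3-6 | No; the stated endpoints are pain and shared decision making |

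Survey size: 1,520 × 0.79 = 1,200.8, which agrees with the 1,200 in section 9.2. That is 1,200/6,900 = 17% of the target intervention-period patients, or 1,200/8,400 = 14% of the maximum.

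**3. Number of visits missed.** The documents give neither an acute-care visit rate nor its timing. For illustration only, assume that 0.5% to 2% of patients have a visit within 7 days and that 20% to 60% of those visits fall on days 4-7. With 6,900 patients, or 6,900/3 = 2,300 per arm:

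- low: 6,900 × 0.005 × 0.20 = 6.9 visits, or 2.3 per arm
- high: 6,900 × 0.02 × 0.60 = 82.8 visits, or 27.6 per arm

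The twelvefold range comes entirely from the assumptions. It shows that the number could be trivial or material and that the documents cannot settle which.

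**4. Event types.** Section 8.2 gathers emergency visits and observation stays, but section 9.4.4 summarises only hospitalisations. Lengthening the window alone would therefore leave two of the three visit types without a planned comparison by arm, even within the first three days.

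**The case against.** The other side has a good deal to say. The window is the same in all four sections, so the plan does not contradict itself, and section 8.3.4 gives a reason for it. Under-controlled pain is measured directly after day 3, by arm, in about 1,200 survey respondents. Inpatient hospitalisation meets the definition of a serious event in section 8.3.2, and section 8.3.6 requires such events to be submitted without a time limit. Details are deferred to a Data Safety Monitoring Plan and to data elements that the DSMB is to define (8.3.5, 8.3.6, 10.1.6). The amendment history records that section 8.2 gained visit types on the DSMB's recommendation. The 7-day order pull is no precedent for a harm window, since the endpoint it serves is a same-day one. Later events are also more often unrelated to the extraction.

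Much of this stands, and it rules out two stronger readings. A reader might infer that harm after day 3 is never captured. The documents do not support that, because the four sources above give partial cover and the separate safety documents cannot be seen here. A reader might also take an assumed spread of durations and infer that most patients stay at risk of a missed visit. With means of 3 to 5 days, a normal distribution with SD 1.5 days puts 50% to 91% still in pain after day 3, and an exponential one puts 37% to 55%. The documents give neither a spread nor a distribution, and having some pain left is not a visit rate.

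The third-molar origin of the 3-to-5-day figure also stands as a limit, because the trial enrols extractions of any permanent tooth. It is nonetheless the only duration the protocol offers, and third molars are among the eligible teeth.

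None of this answers the narrower point. Usual care workflow is not an argument about how long the harm lasts, and no source described in these documents systematically counts acute-care visits after day 3 in all patients.

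**Conclusion.** The concern holds in limited form. As written, systematic capture of acute-care visits and their comparison by arm stop at 72 hours or 3 days, the lower end of the only pain duration the protocol states. At the upper end of that range, 40% of the pain period lies outside the window. The number of visits missed, and whether counting them would change any comparison between arms, cannot be known from the documents.

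The conclusion rests on two assumptions: that the third-molar duration is a fair guide for the enrolled population, and that the separate safety documents do not already extend capture. It does not touch the primary or secondary endpoint analyses. It limits how much reassurance can be drawn from similar 72-hour rates, and the remedy is cheap enough to justify the change.

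**What to change.** In sections 7.1, 8.2, 8.3.4 and 9.4.4, extend the record pull of hospitalisations, emergency department visits and observation stays to 7 days after the index extraction, identically in all three arms. In section 9.4.4, tabulate all three visit types by arm with counts, proportions and confidence intervals, showing days 0-3 and days 4-7 separately. Define the first period so that it reproduces the existing 72-hour hospitalisation figure. Confirm that the Data Safety Monitoring Plan and the DSMB's list of data elements use the same window.

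The change concerns data capture and reporting only. It needs no new patient contact and amounts to a wider date filter on a query already planned. The costs are some additional charts in the existing quarterly review and a larger share of unrelated events among the later ones. The separate tabulation and the existing relatedness review keep that dilution visible.

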8.3.2 DEFINITION OF SERIOUS ADVERSE EVENTS (SAE)

An adverse event (AE) or suspected adverse reaction is considered "serious" if, in the view of either of the co-PIs, it results in any of the following outcomes: (1) death, (2) a life-threatening adverse event, (3) inpatient hospitalization or prolongation of existing hospitalization, (4) a persistent or significant incapacity or substantial disruption of the ability to conduct normal life functions, or (5) a congenital anomaly/birth defect.

Important medical events that may not result in death, be life-threatening, or require hospitalization may be considered serious when, based upon appropriate medical judgment, they may jeopardize the participant and may require medical or surgical intervention to prevent one of the outcomes listed in this definition.

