8.3.6 SERIOUS ADVERSE EVENT REPORTING

Any AE considered serious by a dental provider, study investigator, or PI, or which meets the definition of an SAE included in Section 8.3.2, Definition of Serious Adverse Events must be submitted to PI [name], as soon as possible.

PI [name] or his designee will report necessary SAEs in accordance with HPI Research Subjects Protection Program Standard Operating Procedures at the time of the event. More details about reporting are outlined in the DIODE Data Safety Monitoring Plan.

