8.4.2 UNANTICIPATED PROBLEM REPORTING

The study team member or dental clinic staff will report unanticipated problems (UPs) to Co-investigator [name] or PI [name]. They will submit to Co-investigator [name] to collect and to aggregate. The PI [name] will be responsible for ensuring the assigned Institutional Review Board (IRB) receives notification in accordance with HPI Research Subjects Protection Program Standard Operating Procedures at the time of the event. The UP report will include the following information:

- Protocol identifying information: protocol title and number, PI's name, and the IRB project number;
- A detailed description of the event, incident, experience, or outcome;
- An explanation of the basis for determining that the event, incident, experience, or outcome represents an UP;
- A description of any changes to the protocol or other corrective actions that have been taken or are proposed in response to the UP.

To satisfy the requirement for prompt reporting, UPs will be reported using the following timeline:

- UPs that are serious adverse events (SAEs) will be reported to the IRB and to NIDCR within one week of the investigator becoming aware of the event.

- All UPs should be reported to appropriate institutional officials (as required by an institution's written reporting procedures), the supporting agency head (or designee), and the Office for Human Research Protections (OHRP) within one month of the IRB's receipt of the report of the problem from the investigator.

All unanticipated problems will be reported to NIDCR's centralized reporting system via Rho Product Safety:

- (1) Product Safety Fax Line (US): [name]
- (2) Product Safety Fax Line (International): [contact]
- (3) Product Safety Email: [contact]

General questions about SAE reporting can be directed to the Rho Product Safety Help Line (available 8:00AM – 5:00PM Eastern Time):

- (1) US: [name]
- (2) International: [contact]

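### Quarterly chart review is the only systematic route to single serious hospitalizations with a stated interval, so one could go unassessed for up to about 13 weeks

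*Combined protocol and SAP*

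**What the plan says.** All references are to the combined protocol and SAP.

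- **Review interval (7.1).** The events covered are "Hospitalizations documented within the HealthPartners electronic health record that occur within a 72-hour window following the index extraction encounter". They "will be chart reviewed for severity and relatedness on a quarterly basis during the intervention period". A separate sentence sets the frequency for comparing hospitalization rates: the DSMB's choice or quarterly, whichever is greater.
- **Seriousness (8.3.2).** The criteria for a serious adverse event (SAE), applied in the view of either co-PI, include "inpatient hospitalization or prolongation of existing hospitalization".
- **Handling of SAEs (8.3.6).** An event that a dental provider, investigator or PI considers serious, or that meets the definition, "must be submitted to PI [name], as soon as possible". Necessary SAEs are then to be reported under institutional procedures when the event occurs. Further detail is left to the Data Safety Monitoring Plan.
- **Reporting clock (8.4.2).** Unanticipated problems that are SAEs "will be reported to the IRB and to NIDCR within one week of the investigator becoming aware of the event". Study team members and clinic staff may raise such problems.
- **Sources of information (8.2, 8.3.4).** The EHR is used "Since there are no routine research contacts for all eligible patient participants". The task is to "Gather hospitalizations, emergency department visits, observational bed, and subsequent opioid prescribing made within 3 days post-extraction procedure". Neither section says how often this is done.

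**The concern.** One quarterly activity has to serve two purposes. Comparing admission rates between arms needs accumulated events, and a quarterly interval suits it. Recognizing one serious event and judging whether the intervention contributed needs a short interval, because the reporting duties attach to the single event. Since the clock in 8.4.2 runs from awareness, a long gap before anyone is aware breaks no rule on paper.

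The stake is how quickly a related admission is recognized while the tool remains in use. Section 2.3.1 names the possibility that the tool wrongly attributes a condition or drug to a patient, or that its content is applied without further checking, and lists serious consequences. An admission arising that way may not come to a dental provider's notice, and nothing in the supplied text obliges the provider to find out.

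**Working it through.** The plan states no detection delay, so there is no figure to reproduce. The check compares the possible routes to awareness and then applies interval arithmetic.

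**Routes by which the study could learn of a 72-hour hospitalization**

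| Route | Section | Stated interval | Depends on someone already knowing? |
|---|---|---|---|
| Chart review | 7.1 | Quarterly | No |
| EHR pull | 8.2, 8.3.4 | None given | No |
| Provider contact or feedback button | 8.2 | Ongoing | Yes; prompted by disagreement with the tool |
| SAE submission to the PI | 8.3.6 | Promptly | Yes |
| Problem report by study or clinic staff | 8.4.2 | None for detection | Yes |
| Survey call | 8.3.4 | Once, subsample only | Caller gives information on contacting the dental provider; no event capture described |
| Team meetings | 6.4 | Regular; quarterly with all co-investigators | Yes |
| DSMB | 10.1.6 | At least semiannual | Yes |

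Only the first two rows actively look for admissions across all patients, and only the first has an interval.

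**Delay for an admission found only by the quarterly review**

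- Quarter: 52 / 4 = 13 weeks.
- Maximum wait, for an event just after one review: about 13 weeks.
- Mean wait, with events uniform over the quarter: 13 / 2 = 6.5 weeks.
- With the one-week clock added, where it applies: 13 + 1 = 14 weeks at most, 6.5 + 1 = 7.5 weeks on average.

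**Patients treated in one interval**

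Inputs: 6,900 intervention-period patients (9.2); 12 months or until accrual is met (6.1.1), or weeks 53 to 116, which is 64 weeks (1.3); 1:1:1 allocation of providers (4.1). Assumptions: steady accrual and equal patient volume per arm.

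| Duration | Per week | Per 13 weeks | Two tool arms (2/3) |
|---|---|---|---|
| 52 weeks | 6,900 / 52 = 132.7 | 1,725 | 1,150 |
| 64 weeks | 6,900 / 64 = 107.8 | about 1,400 | about 930 |

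**Workload**

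The documents give no hospitalization rate. For an assumed 0.1% to 0.5% over a 52-week period:

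- 6,900 x 0.001 = 6.9 charts a year; 6,900 x 0.005 = 34.5.
- Divided by 12: about 0.6 to 2.9 charts a month.

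The delay figures do not depend on this assumption.

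**The case against.** The strongest counter-argument is that 7.1 fixes the interval for adjudicating severity and relatedness, not for first seeing the event. The EHR pull is described separately, and if it runs more often, someone may be aware well before the quarterly review. The Data Safety Monitoring Plan, to which 8.3.5 and 8.3.6 refer for reporting detail, may say so. This stands as a limit: neither the pull frequency nor that plan can be checked here. It does not remove the point, because the only interval in the protocol is quarterly and would need aligning with any faster practice.

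Three stronger readings are tempting, and the documents do not support them.

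- **That every hospitalization starts the one-week clock.** The clock covers only SAEs that are also unanticipated problems. Under 8.4.1 these must be unexpected, at least possibly related, and suggestive of greater risk. Section 8.3.3.3 classes inadequately controlled pain, drug interactions and analgesic side effects as expected, though unusual severity or frequency can still make an event unexpected. Few admissions may qualify. However, 7.1 places the judgment of relatedness in the quarterly review, so which ones qualify may not be known until then.
- **That nobody looks for a quarter.** Section 2.3.1 relies on pre-launch testing and continuing provider feedback; 6.4 provides regular meetings on technical functioning; 8.2 and 8.3.6 give providers direct routes. A display fault can surface without any admission. The remaining weakness is that the feedback instruction is triggered by disagreement with the tool, so a provider who follows an erroneous display has nothing to report.
- **That the patients treated in a quarter measure harm.** They are everyone with an index extraction in that time, not patients affected by a fault.

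The protocol also describes the intervention as minimal risk, leaves prescribing to provider judgment and has an independent DSMB. That bears on how serious the gap is, not on whether it exists.

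**Conclusion.** The concern holds as a gap in detecting single events. It is not a breach of the reporting rule. Because no other systematic route has an interval, a hospitalization not reported earlier could remain unassessed for up to about 13 weeks, in tension with the promptness that 8.3.6 asks for. Where such an event turns out to be a serious unanticipated problem, its clock may start only at that review. The maximum follows from the quarterly interval; the mean needs events spread evenly over the quarter. The exposure range is conditional on steady accrual and equal volume per arm. The conclusion would weaken if the Data Safety Monitoring Plan or operating practice already sets a shorter interval for the EHR pull. This is a worthwhile, inexpensive improvement, and no threat to the efficacy analyses.

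**What to change.** In 7.1, separate the two tasks:

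1. **Single-event detection.** Run the EHR hospitalization query more often than quarterly, for example monthly, and chart review each hit for severity and relatedness on receipt. State that awareness for 8.4.2 dates from receipt at the latest. A monthly query cuts the maximum wait to 52 / 12 = about 4.3 weeks and the mean to about 2.2.
2. **Rate comparison between arms.** Leave it at the frequency now stated.

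Give the query frequency in 8.2 and 8.3.4, and align 7.1, 8.3.6 and the Data Safety Monitoring Plan with it. If that plan already sets a shorter interval, carrying it into 7.1 is enough.

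The cost is protocol wording and more frequent scheduling for the query and the reviewer. The total number of charts is the same, and the efficacy analyses do not change. The documents do not describe query set-up or staffing, so the sponsor should confirm that the extra runs need no added resources.
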